3.5.3 Immunogenicity Assessments

Anti-drug antibody (ADA) sampling will be performed at the time points shown in Appendix 6.1 Table 8 (Part A) and Table 9 (Part B). ADA-positive or ADA-negative will be determined for each time point. If the first test comes back positive then the reactivity to the CCI

CCI [REDACTED] will be assessed separately. Titers will be determined for ADA positive sample if the quantity is sufficient for the determination. If Screening tier is Negative then ADA response is Negative at the corresponding visit. If Screening tier is Positive then ADA response is Confirmatory Tier response (Positive, Negative or QNS (quantity not sufficient) at the corresponding visit.

3.5.4 Pharmacodynamic Assessments

CCI [REDACTED]

3.5.5 Other Assessments

3.5.5.1 Informed Consent

An ICF must be signed by prospective patients prior to initiating any study-specific procedures.

3.5.5.2 Inclusion and Exclusion Criteria

Inclusion and exclusion criteria will be reviewed for each potential patient. Eligibility will be documented in the eCRF (for more information refer Protocol section 5).

3.5.5.3 Demographics, Celiac Disease History and Medical History

Complete medical history will be obtained, including demographics, symptoms at diagnosis, disease history, and length of time on a GFD.

3.5.5.4 [REDACTED]

CCI [REDACTED]

CCI

3.5.5.5 GC (Part B only) Administration

Dates and times will be captured for GC administration on D15, D16, and D17. Patient compliance will be recorded by the study Investigator.

4 STATISTICAL METHODS

The following treatment groups will be considered for reporting for each part, except for PK reporting:

Part A (SAD)

- KAN-101 0.15 mg/kg
- KAN-101 0.30 mg/kg
- KAN-101 0.60 mg/kg
- KAN-101 1.20 mg/kg
- KAN-101 1.5 mg/kg
- Pooled KAN-101

Part B (MAD)

- Pooled Placebo
- KAN-101 0.15 mg/kg
- KAN-101 0.30 mg/kg
- KAN-101 0.60 mg/kg
- Pooled KAN-101

All summary tables will be presented for Part A and Part B separately (unless otherwise specified). Also, summary tables will be presented for Part A and Part B combined for the same dose level treatment group for the following:

- PK data: PK concentrations and parameters for Day 1 in 0.15, 0.30, and 0.60 mg/kg dose levels will be summarized using descriptive statistics
- Disposition, analysis population, demographics, baseline celiac disease, ADA, and Treatment-Emergent Serious Adverse Events (TESAEs).

Listings will be presented for subjects from Part A and Part B to display the collected data of clinical and statistical importance. All by-subject listings will include part, treatment group,

center, and subject ID for enrolled subjects. All TLFs will be analyzed by dose level received and not by cohort number.

The principal of ‘As Treated’ (as dose level received) will be applied to the subject treatment data. If there are randomization or cohort assignment errors they will still be analyzed in the treatment group of the dose level they received. If the actual dose level received is unknown then the subject will be analyzed under the planned dose level, however for PK TFLs, the concentrations and parameters from such subject/s will be listed and flagged in the Listings, but excluded from summary tables and statistical analysis, since these are not pharmacokinetically meaningful if the dose is unknown.

4.1 Data Quality Assurance

All TLFs data to be included in the report will be independently checked for consistency, integrity and in accordance with standard Parexel procedures. Datasets will be prepared using headings from Clinical Data Interchange Consortium (CDISC) Study Data Tabulation Model (SDTM) implementation for human clinical trials and Analysis Dataset Model.

4.2 Changes in the SAP Compared to the Study Protocol

No changes.

4.3 General Presentation Considerations and Descriptive Statistics

No formal statistical hypotheses or inferential statistics will be performed in this study. For Part A and Part B, summary statistics and listings will be provided by dose.

All by-visit summaries will be based on the nominal day/time per Appendix 6.1 [Table 8](#) (Part A) and [Table 9](#) (Part B) as recorded on the eCRF.

Study day will be calculated relative to the date of first dose, ‘Study Day’ = Assessment Date – First Dose Date + 1.

4.3.1 Non-PK Tables, Listings and Figures

- ‘Baseline’ is defined as the last available pre-treatment assessment, including any unscheduled assessment. Every effort will be made to ensure that accurate baseline information is collected. Subjects will not be excluded from any of the analysis populations due to missing baseline. However, if a subject is missing baseline information, they will have a missing change from baseline result.
- Continuous data will be summarized in terms of the number of observations (n), mean (arithmetic), standard deviation (SD), median, and range (minimum and maximum), unless otherwise stated.
- The minimum and maximum will be reported to the same number of decimal places as the raw data recorded in the database. The mean and median will be reported to one more decimal place than the raw data recorded in the database. The SD will be reported to two more decimal places than the raw data recorded in the database. In general, the maximum number of decimal places reported shall be four for any summary statistic.
- Categorical data will be summarized in terms of the number of subjects providing data at the relevant time point (n), frequency counts and percentages.

- Percentages will be rounded to the nearest one decimal place. Percentages will not be presented for zero counts. Percentages will generally be calculated using the number of subjects in a group (n) as the denominator, otherwise the method will be noted in a footnote.
- Unscheduled and early termination visits may not be summarized in the tables but will be presented in the listings.

4.3.2 PK Tables, Listings and Figures

The following rules will be followed with regards to the number of decimal places and presentation of data in the tables and listings for PK concentration data:

- Source data shall be used in all derived PK concentrations without prior rounding.
- The mean, SD, geometric mean and median will be tabulated to same significant digit compared to the source data, but with a maximum of four significant digits.
- Minimum and maximum values will be tabulated to the same precision as the source data, but with a maximum of four significant digits.
- Geometric coefficient of variation (geometric CV%) and arithmetic coefficient of variation (CV%) will be presented to one decimal place.

The following rules will be followed with regards to the number of decimal places and presentation of data in the tables and listings for PK parameters:

- Individual PK parameters will be presented to three significant digits, with the exception of t_{max} , which will be presented to three decimal places.
- Parameters derived directly from source data (e.g. C_{max}) shall be reported with the same precision as the source data (if this is not four significant digits).
- The mean, geometric mean, median and SD values will be reported to three significant digits, all other descriptive statistics will also be reported to three significant digits except for CV% and geometric CV% which will be presented to one decimal place.
- For t_{max} , the minimum and maximum will be presented to three decimal places and all other descriptive statistics will be presented to three decimal places.
- Estimates and confidence intervals in the form of percentages will be presented to two decimal places.

4.4 Analysis and Data Handling Conventions

4.4.1 Multi-center Studies

The term 'Center' will be used to define each investigator site. The data from all study centers (approximately 5 to 12 US sites) will be pooled together for analyses and summary statistics.

4.4.2 Adjustments for Covariates

No adjustments for covariates are planned for the study.

4.4.3 Handling of Dropouts or Missing Data

All missing or partial data will be presented in the patient data listing, as they are recorded on the eCRF. Patients lost to follow-up or withdrawn will be included in statistical analyses up to the point of their last evaluation.

4.4.3.1 Missing Start and Stop Dates/Time for Adverse Events

Due diligence will be done to obtain accurate AE information. If all planned methods to obtain accurate time AE information have failed, missing and partial AE onset and end dates will be imputed. Imputed dates will be flagged in the individual supportive subject listings. Unless otherwise specified, the following conventions will be used:

Missing and Partial AE onset dates:

- If onset date is completely missing, then onset date is set to date of first dose.
- If onset year is present and
 - month and day are missing:
 - If onset year = year of first dose, then set onset date to date of first dose.
 - If onset year < year of first dose, then set onset month and day to December 31st.
 - If onset year > year of first dose, then set onset month and day to January 1st.
 - month is missing:
 - If onset year = year of first dose, then set onset date to date of first dose.
 - If onset year < year of first dose, then set onset month to December.
 - If onset year > year of first dose, then set onset month to January.
- If onset month and year are present and day is missing:
 - If onset year = year of first dose and
 - onset month = month of first dose then set onset date to date of first dose.
 - onset month < month of first dose then set onset date to last day of month.
 - onset month > month of first dose then set onset date to 1st day of month.
 - If onset year < year of first dose, then set onset date to last day of month.
 - If onset year > year of first dose, then set onset date to 1st day of month.
- For all other cases, set onset date to date of first dose.

Missing and Partial AE end dates:

- If end date is completely missing, end date is not imputed and the AE is flagged as “ongoing”.
- If year is present and
 - month and day are missing:
 - If year = year of last dose, then set end date to the date of last dose.
 - If year < year of last dose, then set end month and day to December 31st.
 - If year > year of last dose, then set end month and day to January 1st.
 - month is missing:
 - If year = year of last dose, then set end date to date of last dose.
 - If year < year of last dose, then set end month to December.
 - If year > year of last dose, then set end month to January.

- If month and year are present and day is missing:
 - If year = year of last dose and
 - month = month of last dose then set day to day of last dose.
 - month < month of last dose then set day to last day of month.
 - month > month of last dose then set day to 1st day of month.
 - If year < year of last dose, then set end date to last day of the month.
 - If year > year of last dose, then set end date to 1st day of month.
- For all other cases, set end date to date of last dose.
- Screen failures are collected in EDC and will be a part of SDTM. Screen failure data are not analyzed and will not be included in the ADaM except for demographics (ADSL) and inclusion/exclusion criteria (ADIE).

Any AEs with incomplete start and end dates/times will be treated as follows:

- Adverse events with unknown start and/or end times (but where the date is known) will be imputed with a time of 00:00 h for the tabulations but will be shown as NK: NK in the listings (where NK = Not Known).

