3.5.1.1 Adverse Events (AE)

All AEs from the time of signing of Informed Consent Form (ICF) through the final Follow-Up Visit/phone call will be collected. Adverse events will be coded using the Medical Dictionary for Regulatory Activities (MedDRA) Version 23.1 (MedDRA Sep 2020) or higher. Ongoing AEs considered at least possibly related to KAN-101 treatment should be followed until resolution, return to baseline, or are considered stable or chronic.

AE:

An AE is defined as any untoward medical occurrence associated with the use of a drug, or with study participation, whether or not consider related to study treatment.

TEAE:

TEAEs are defined as AEs that emerge or worsen in the period from the first dose of study treatment to the final Follow-Up Visit/phone call after the last dose study drug.

The incidence and severity of TEAEs as assessed by the CTCAE v5.0 or higher is considered the primary endpoint. TEAEs that occur before and after gluten challenge will also be examined separately and defined as in section 4.8.1.

DLT:

A dose-limiting toxicity (DLT) for Study KAN-101-01 is defined as any \geq Grade 3 AE assessed as related to KAN-101 or Grade 2 AE assessed as related to KAN-101 not resolving within 14 days. DLTs do not include those AEs attributable solely to intercurrent illness or other concomitant medications.

AE Severity:

The National Cancer Institute Common Toxicity Criteria Adverse Event (NCI-CTCAE) version 5.0 or higher will be used to grade the severity of all AEs, whether or not they are considered related to KAN-101. Toxicities that are not specified in the NCI-CTCAE will be defined as follows:

- Grade 1: Mild; asymptomatic or mild symptoms; clinical or diagnostic observations only; intervention not indicated
- Grade 2: Moderate; minimal, local or noninvasive intervention indicated; limiting age-appropriate instrumental activities of daily living (ADL)
- Grade 3: Severe or medically significant but not immediately life-threatening; hospitalization or prolongation of hospitalization indicated; disabling; limiting self-care ADL
- Grade 4: Life-threatening consequences; urgent intervention indicated
- Grade 5: Death related to AE

AE Causality:

Relationship to the study drug for all AEs will be assessed as “drug related” (Possible, Probable, Definite) or “not drug related” (None, Remote).

Impact of COVID-19:

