4.4.3.2 Missing Start and Stop Dates for Prior and Concomitant Medication

For the purpose of inclusion in prior and/or concomitant medication tables, incomplete medication starts and stop dates will be imputed as follows:

- If year and month are present and day is missing, then set day to first day of month for start date and set day to last day of month for end date.
- If year and day are present and month is missing, then set month to January for start date, and set month to December for end date.
- If year is present and month and day are missing, then set month and day to January 1 for start date and set month and day to December 31 for end date.
- Completely missing date will not be imputed.

The partial dates will be provided as such in the subject data listings (with the imputed dates).

When imputing a start date, the programmer will ensure that the new imputed date is sensible i.e. it is before the end date of prior and concomitant medications.

4.4.3.3

CCI

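### The adverse-event onset rule defaults to the first-dose date without checking a recorded end date, so an event known to have ended before dosing would be classed as treatment-emergent

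*SAP*

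**What the plan says.** SAP 3.5.1.1 starts collection before treatment: "All AEs from the time of signing of Informed Consent Form (ICF) through the final Follow-Up Visit/phone call will be collected". Protocol synopsis, Study Duration, allows a screening period of up to 28 days, so pre-dose events will be in the adverse-event data. The same SAP section separates them from treatment-emergent events: "TEAEs are defined as AEs that emerge or worsen in the period from the first dose of study treatment". It names TEAE incidence and severity as the primary endpoint.

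SAP 4.4.3.1 sets the onset to the first-dose date in these situations:

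- Nothing is known: "If onset date is completely missing, then onset date is set to date of first dose".
- The month is missing, with or without the day: "If onset year = year of first dose, then set onset date to date of first dose".
- Only the day is missing and the year matches: "onset month = month of first dose then set onset date to date of first dose".
- Anything left over: "For all other cases, set onset date to date of first dose".

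An onset with only the day missing, in an earlier month of the first-dose year, is treated differently: "onset month < month of first dose then set onset date to last day of month". Onsets in an earlier year are likewise placed before dosing.

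For medications, SAP 4.4.3.2 adds a consistency check: "When imputing a start date, the programmer will ensure that the new imputed date is sensible i.e. it is before the end date". Section 4.4.3.1 has no counterpart for adverse events.

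**The concern.** Defaulting an unknown onset to the first dose is a normal conservative choice when nothing in the record contradicts it. The difficulty arises when something does. If the end date is recorded and falls before the first dose, the event is known to be pre-treatment, yet the rule gives it an onset on Day 1. The record then shows an event that ended before it began. A programmer who derives TEAE status from the imputed onset would count it.

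The affected output is the primary endpoint, tabulated in very small groups, so one patient is visible in the percentages. In Part B a Day 1 onset would also put the event in the summary of TEAEs before the gluten challenge (SAP 4.8.1). The SAP applies the needed safeguard to medications but not to the data that feed its primary endpoint, which suggests an oversight.

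**Working it through.** The documents give no figure to reproduce here, so the check applies the rule as written.

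**Step 1: worked example.** Assume first dose on 20 May 2021 and a recorded end date of 12 May 2021.

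| Recorded onset | Imputed onset (SAP 4.4.3.1) | On or after first dose? | Later than recorded end? |
|---|---|---|---|
| completely missing | 20 May 2021 | yes | yes, by 8 days |
| 2021 only | 20 May 2021 | yes | yes, by 8 days |
| day 8, month missing, 2021 | 20 May 2021 | yes | yes, by 8 days |
| May 2021, day missing | 20 May 2021 | yes | yes, by 8 days |
| April 2021, day missing | 30 April 2021 | no | no |

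The first four patterns become TEAEs by imputed onset although the event was over 8 days before dosing. The fifth does not.

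**Step 2: how far each branch reaches.** Take every first-dose day of a 365-day year and a true onset on each of the 28 preceding days: 365 × 28 = 10,220 combinations, all truly pre-dose with a known pre-dose end. The share moved to the first-dose date is:

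- onset completely missing: 10,220/10,220 = 100%
- year only: 9,814/10,220 = 96.0%
- month missing, day and year known: 9,814/10,220 = 96.0%
- day missing only: 5,348/10,220 = 52.3%

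The exceptions are onsets in an earlier calendar year or, when only the day is missing, in an earlier month. These shares assume full 28-day screening and evenly spread dates. They describe what the rule does to such a record, not how often one occurs.

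**Step 3: size in the tables.** Group sizes come from SAP 3.2: 3 or 6 per Part A cohort, and 6 active and 2 placebo per Part B cohort over 3 cohorts. Pooled placebo is 3 × 2 = 6 and pooled Part B KAN-101 is 3 × 6 = 18. For one misclassified patient with no other TEAE, the shift is 1/n:

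- Part A group of 3: 1/3 = 33.3 points
- Part B active group of 6, or pooled placebo: 1/6 = 16.7 points
- Part B pooled KAN-101: 1/18 = 5.6 points

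Groups are by dose level received (SAP 4). If the patient has another TEAE, any-TEAE incidence does not move, though counts by preferred term or severity could.

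**Step 4: with the end-date check added.** The four misclassified patterns in Step 1 become non-treatment-emergent. In Step 2, misclassification of events with a known pre-dose end falls to 0% in every branch.

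**The case against.** The strongest reply is that such an event fails the TEAE definition itself: something that ended before the first dose neither emerged nor worsened after it. The SAP does not say that TEAE status is derived from the imputed onset alone. That is fair. It is why the claim here is that the event would be counted if the rule is applied literally, not that it certainly will be. But the SAP does not say which prevails, and the imputation rule is the only operational instruction given.

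The second reply is rarity and visibility. Protocol 11.2.1 requires the investigator to assign onset and resolution dates and to review events at each visit. Imputation is used only after attempts to obtain the date have failed. Imputed dates are flagged in listings, the listings show onset, end and duration (SAP 4.8.1), outputs are checked for consistency (SAP 4.1), and data issues are resolved before lock (SAP 4.4.8). All of this lowers the likely number of records, possibly to zero. None of it tells anyone to reclassify the event in the tables.

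Third, the analysis is descriptive (SAP 4.3), the rule is the same for KAN-101 and placebo, and it adds events rather than removing them. This stands and keeps the point minor. An extra placebo event could narrow an apparent difference, but no real event is lost.

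**Conclusion.** The rule as written gives a wrong result for a specific kind of record: a screening event whose recorded end precedes the first dose and whose onset is wholly missing, matches the first-dose year (month missing) or month and year (day missing), or falls in the catch-all. The point shifts in Step 3 assume one such record in a patient with no other TEAE. The number of records is unknown and probably small, so the severity is low.

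A reader might infer more than the documents support:

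- **That every partial onset is affected.** Those in an earlier month or year stay before dosing.
- **That the problem is common because the pre-dose window is long.** With full screening, 28/(28+28) = 50% of collection days in Part B and 28/(28+21) = 57% in Part A precede dosing. But 28 days is a maximum, and a share of days says nothing about how many events lack an onset yet have an end date.
- **That drug-related or DLT counts are inflated.** Relatedness is the investigator's judgement and requires an association with KAN-101 administration (Protocol 11.2.2). An event that ended before any dose should not meet it, and a DLT requires relatedness.

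**What to change.** Add to SAP 4.4.3.1, mirroring 4.4.3.2:

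*If the recorded end date, or the recorded parts of a partial end date before any imputation, show that the AE ended before first dose, the AE is not treatment-emergent. An imputed onset may not be later than a known complete end date; where it would be, set onset to that end date.*

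Keep the first-dose default in all other cases. The test must use the recorded parts of a partial end date because 4.4.3.1 also imputes end dates, in some branches to the last-dose date, and an imputed end is not evidence of when the event stopped. With first dose on 20 May, a recorded end of April settles the matter; a recorded end of May does not, and the default stays.

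The cost is two sentences in the SAP and a small change to the adverse-event dataset derivation. No data collection, clinical procedure or other analysis changes.

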4.8.1 Adverse Events

For Part A (SAD) and Part B (MAD) separately, the following AE summaries will be provided for the number of subjects reporting at least one AE by treatment group using the ATAS:

- An overall summary of TEAE will include the number of subjects with any TEAEs, drug-related TEAEs, \geq Grade 3 TEAEs, TESAEs, TEAEs leading to discontinuation (treatment and study);
- Before and after GC, overall summary of TEAE will include the number of subjects with any TEAEs, drug-related TEAEs, \geq Grade 3 TEAEs, treatment-emergent serious AEs (TESAEs), TEAEs leading to discontinuation (treatment and study); (this table is for Part B only);
- A summary of the number and percentage of subjects reporting a TEAE by system organ class (SOC) and PT;
- A summary of the number and percentage of subjects reporting a TEAE by causality, SOC and PT;
- A summary of the number and percentage of subjects reporting a TEAE by severity, SOC and PT.

AE summaries will be ordered in terms of decreasing frequency for SOC, and PT within SOC, in the Total group, and then alphabetically for SOC, and PT within SOC.

For each subject and each AE, the worst severity recorded will be attributed and used in the by-severity summaries. Similarly, the worst causality (most related to treatment) will be attributed and used in the by-causality summaries.

CCI

CCI

A summary of TESAE will be presented for Part A and B combined.

For Part A and Part B, by-subject listings of AEs will be presented by study part and treatment group for the following listings:

- All DLT events
- All TEAEs
- All SAEs
- All TESAEs
- TEAEs Leading to Study Discontinuation
- TEAEs Leading to Permanent Discontinuation of Study Drug

The following information will be included in the listings: verbatim (reported term), PT, SOC, AE onset date (and time), AE end date (and time), AE duration, relationship to study drug, AE outcome, severity and SAE indicator flag. If available, confirmed and suspected SARS-CoV-2 infections and/or COVID-19 cases will be recorded in the AE eCRF and data will be presented.

Pandemic related Impact of COVID-19 will be presented in listing, detailing the category of impact (example: Missed Visit, Missed Assessment, Early termination, Screen Failure, Adverse Event, Withdrawal of consent, Death, Replacement subject) based on data availability.

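### Unknown AE times are set to 00:00 with no exception for the first-dose day, and missing or partial onset dates default to before the gluten challenge

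*SAP*

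**What the plan says.** SAP 4.4.3.1 has two sets of onset rules.

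- **Time rule.** Where the date is known but the start or end time is not, the event "will be imputed with a time of 00:00 h for the tabulations". Listings show the time as not known. Neither the day of first dose nor Day 15 is exempted.
- **Date rules.** A completely missing onset date becomes the date of first dose. With the day missing in the year of first dose, the instruction is "onset month = month of first dose then set onset date to date of first dose". A later month goes to its 1st day.

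These rules feed two classifications.

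- **Treatment-emergence.** SAP 3.5.1.1 states: "TEAEs are defined as AEs that emerge or worsen in the period from the first dose of study treatment". It also states: "The incidence and severity of TEAEs as assessed by the CTCAE v5.0 or higher is considered the primary endpoint". It does not say whether the comparison with first dose uses the date alone or the date and time.
- **The gluten-challenge (GC) split in Part B.** SAP 3.5.1.1 states: "TEAEs that occur before and after gluten challenge will also be examined separately and defined as in section 4.8.1". Section 4.8.1 specifies the table ("Before and after GC, overall summary of TEAE will include the number of subjects with any TEAEs"). Its visible text gives no definition of the split, and parts of the section are redacted.

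**The concern.** Midnight on Day 1 comes before a daytime infusion. If the derivation compares clock times, a reaction after the infusion with no recorded time is dated before first dose and is not a TEAE. The primary endpoint would then lose drug reactions on the first dosing day. Protocol 1.2 describes symptom onset within hours for earlier intradermal peptides, and the patient given 1.5 mg/kg had symptoms like those of gluten ingestion.

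The before/after GC table exists to separate events in the drug period from events after gluten. A default that moves uncertain onsets to the early side credits gluten reactions to the drug-only period.

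**Working it through.** No figure in the plan rests on this rule, so there is none to reproduce. The check is a reading of the rules, followed by calendar arithmetic.

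**1. Where the imputed time can act.** The time rule is for tables. The visible AE tables in SAP 4.8.1 are counts of subjects; clock times and AE duration appear only in listings. In the visible plan, an imputed time can therefore change a table only by placing an event relative to the dose or the challenge.

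**2. Both readings of the comparison.** The documents give no clock time for dosing or challenge, so starts at 08:00, 09:00 and 14:00 were assumed. All three give the same result.

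| Untimed event dated | Date and time compared | Date only |
|---|---|---|
| D1 | before first dose, not a TEAE | TEAE |
| D4 | TEAE | TEAE |
| D15 | TEAE, before GC | TEAE, not before GC |
| D16 | TEAE, after GC | TEAE, after GC |

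Total TEAE incidence can change only through D1. D15 affects only the before/after GC table.

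**3. Consistency within 4.4.3.1.** An event with no date at all is sent to the first-dose date, which makes sense only if such events are meant to count as treatment-emergent. Under a date-and-time comparison, an event known to have occurred on that date but untimed would be excluded. The better-documented event would be the one lost.

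**4. Day-missing dates and the GC split (no clock time needed).** Let first dose fall on day d of a month. D15 is day d + 14.

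- 31-day month: D15 is in the same month if d ≤ 17 (17/31 = 55%). A D15 reaction with the day missing is imputed to D1, before GC.
- For d from 19 to 31, D15 falls on the 2nd to the 14th of the next month. The reaction is imputed to the 1st, again before GC.
- Only d = 18 escapes, because D15 is itself the 1st. Total before GC: 17 + 13 = 30 of 31.
- 30-day month: d ≤ 16 (16/30 = 53%) goes to D1, d from 18 to 30 goes to the 1st, and d = 17 escapes. Total: 16 + 13 = 29 of 30.

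Completely missing dates always go to D1. The day-missing error runs one way. A pre-challenge event can fall in the next month only if D15 is later than the 1st, and the imputed 1st is then still before the challenge.

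**5. Size.** One patient is 1/3 = 33 percentage points in an initial Part A cohort of 3 and 1/6 = 17 points among the 6 active patients of a Part B cohort. The tables count subjects with at least one event, so overall incidence moves by that much only if the lost event is the patient's sole TEAE. Otherwise only the rows for that event change.

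**The case against.** The strongest reply is that treatment-emergence is probably judged by date. Study day is calculated from dates (SAP 4.3). Medications that continue across first dose are classified against its date (SAP 3.5.1.2.5). The missing-date rule works as intended only if an onset on the first-dose date counts. The 00:00 rule applies only where the date is known, so an imputed date has no stated time to compare. On that reading no Day 1 event is lost. This stands as far as it goes: the loss is conditional. It does not close the point, because the SAP never states the date-level rule and step 1 leaves the imputed time no other visible role in a table.

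A reader might infer that primary TEAE counts are wrong at both dividing lines. The documents do not support that. A Day 15 event is treatment-emergent on either side of the challenge, so the split cannot change total incidence. The definition of the split may lie in the redacted part of 4.8.1, and its absence from view is not a fault.

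Three further replies also hold. Patients are observed for 10 hours on D1, with a phone call at about 24 hours, and for at least 6 hours on D15, so most onsets in those windows should be timed. Imputation applies only after efforts to obtain the information have failed. DLTs are defined by grade and relatedness, not by TEAE status, so nothing here shows that escalation decisions are affected.

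**Conclusion.** The plan contains a rule that can give a wrong result, and its effect on the primary endpoint is conditional. If TEAE status is derived by date and time, untimed Day 1 reactions after the infusion drop out of the primary TEAE tables, against the intent of the SAP's own missing-date rule. If it is derived by date, they do not. It would go too far to say that the primary endpoint is shown to be miscounted.

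The missing- and partial-date problem does not depend on clock times, but it is confined to the before/after GC table. There, day-missing Day 15 reactions are placed before the challenge for 30 of 31 (or 29 of 30) first-dose days, and completely missing dates always are. An untimed Day 15 event joins them only if clock times are compared. All of this is subject to any different rule in the redacted text of 4.8.1.

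The documents do not give the number of affected events, and it is probably small. The 33- and 17-point shifts are the effect of a single event that is the patient's only TEAE; they are not an expected bias.

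**What to change.** Make two changes to SAP 4.4.3.1 and the matching derivations before database lock.

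1. State that an AE dated on the first-dose date with unknown time is treatment-emergent unless the source shows onset before the infusion, and that 00:00 is not applied to onset on that date.
2. For the before/after GC table, place any AE whose missing or partial date, or unknown time, leaves it possible on either side of the first gluten dose in a 'period not determinable' row, not under 'before GC'. If the redacted part of 4.8.1 already sets a rule, refer to it here and make the two agree.

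The cost is two sentences, a small programming change and one extra table row, with no new data. The downside is a slightly more inclusive TEAE count, since an untimed Day 1 event that truly began before the infusion would be counted unless the source shows it.
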